9.3 Interim analyses and Stopping

Since the overall safety of both general and local anesthesia have long been established and both techniques are considered reasonable standard of care, we plan for a single interim analysis once 50% enrollment is reached. We will not employ formal stopping rules, given the incredibly low likelihood of this necessity. However, as outlined above, we will temporarily halt enrollment if 3 AE occur so that we can identify potential causes before proceeding.

If an interim analysis is planned, describe the rationale, effect on “spending” the Type I error, and method for adjusting calculations. As relevant, provide guidelines for stopping the study for reasons of efficacy, safety, futility, or poor study performance (e.g., slow accrual, high losses-to-follow-up, and poor quality control).

Describe safety findings and statistical rules that would temporarily suspend enrollment and/or study intervention until a safety review is convened (either routine or ad hoc) to determine whether the study should continue per protocol, proceed with caution, be further investigated, be discontinued, or be modified and then proceed.

Examples of findings that might trigger a safety review are the number of SAEs overall, the number of occurrences of a particular type of SAE, severe AEs/reactions, or increased frequency of events. Such findings are presented to the study statistician or to the Data and Safety Monitoring Board (DSMB) statistician to review the events by group to determine whether there are statistical as well as clinical concerns. The statistician reports his findings to a closed session of the DSMB or to the Safety Officer and/or NIA. The findings are used to determine what steps will be taken.

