7.1.1 Definition of adverse events (AE)

Adverse event means any untoward medical occurrence associated with the use of an intervention in humans, whether or not considered intervention-related (21 CFR 312.32(a)).

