7.5 Safety Monitoring

The NIA Guidelines on Data and Safety Monitoring generally require that a NIA-appointed Data and Safety Monitoring Board or Safety Officer monitor clinical trials. Please see the Safety Monitoring Guidelines (a link will be inserted here).

Inguinal hernia repair is generally considered a safe procedure with very few (<1% risk of E).^{3,7,8} Both local and general anesthesia are considered reasonable standard of care for the operation, and there are generally few AE or SAE resulting directly from the anesthesia modality. Most complications, AE, SAE, or UP result from the surgery rather than anesthesia, and the surgical technique is the same for both study arms. Consequently, we will convene our data safety and monitoring board to review all AE, SAE, and UP once 50% of expected enrollment is obtained. The UT Southwestern Department of Surgery maintains a standing DSMB for monitoring of all trials in our department. Given that all published studies of local versus general anesthesia have been completed without significant rates of adverse events or early termination, it is highly unlikely that the use of stopping rules will be required.

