8 INTERVENTION DISCONTINUATION

The study will be halted if three grade 3 AEs are identified and determined to be probably related or definitely related to the study interventions (distinct from surgical complications). The PI will notify NIA and the IRB immediately when the third grade 3 event is reported, and enrollment screens will stop accepting new study participants.

Participants may voluntarily withdraw/stop participation at any time and for any reason (noted on consent form). If participants withdraw, we will make every effort to obtain permission and convince them to complete planned evaluations and will try counseling patients to re-enroll in the study if possible. We will also make every effort to continue monitoring and treating AE/SAE for participants who withdraw.

There will be no replacement of participants who withdraw early. Additionally, we will continue to follow participants, with their permission, even if the study intervention is discontinued.

List criteria for discontinuing the study intervention/product (e.g., development of toxicities, study closure by institute) for a participant and methods for determining when criteria are met.

If relevant, include criteria for temporary discontinuation of treatment and define its length.

Also note that subjects may withdraw voluntarily from participation in the study at any time and for any reason. Participants should continue to be followed, with their permission, even if the study intervention is discontinued. Discuss any modifications to the schedule and duration of continued follow-up and indicate the evaluations to be completed while the participant is either temporarily or permanently discontinued from study intervention but followed for outcomes, if applicable.

This section should also include a discussion of replacement of subjects who discontinue early, if replacement is allowed.

Note: It is vital to collect safety data on any subject discontinued due to an AE or SAE. In any case, every effort must be made to undertake protocol-specified safety follow-up procedures. If voluntary withdrawal occurs, the subject should be asked to continue scheduled evaluations, complete an end-of-study evaluation, and be given appropriate care under medical supervision until the symptoms of any AE resolve or the subject's condition becomes stable.

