9.2.1 Treatment Assignment Procedures

We will randomly assign older patients having inguinal hernia surgery to one of the two study arms: (1) local anesthesia or (2) general anesthesia. Our goal for enrollment will be a total of 80 participants with 40 participants in each arm and a total of 40 participants from each site. We will use a stratified randomization scheme with blocking within strata. Stratification factors include hospital location (Dallas or Houston) and age (65-75 or 75+ years). Equal allocation by strata will be used so that differences among hospitals and age groups will be balanced. Randomized assignments will be generated ahead of time for each combination of strata and placed within stored and numbered envelopes kept at each hospital location. We will generate 20% more assignments than necessary to allow for potential withdrawals. Before patients are enrolled, physicians, patients, and research coordinators will not know which anesthesia modality will be assigned. Once patients are enrolled, the next envelope that applies to that participant (based on stratification factors) will be selected and labeled with the date and time of enrollment, the patient’s name, and the research team member responsible for enrollment. The labeled and unopened envelope will be photographed for our records and the envelope number will be recorded in the participant’s record.

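### Sections 8 and 9.3 state the safety halt differently: three related grade 3 events halt the study in one, any three adverse events pause enrollment in the other

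*Combined protocol and SAP*

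**What the plan says.** **Section 8 (Intervention Discontinuation).** The rule here reads "The study will be halted if three grade 3 AEs are identified and determined to be probably related or definitely related". Relatedness is judged against the anesthesia interventions under study, and surgical complications are set apart. At the third event the principal investigator notifies the NIA and the IRB, and "enrollment screens will stop accepting new study participants". No restart condition follows.

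**Section 9.3 (Interim analyses and Stopping).** One interim analysis is planned at 50% enrollment. The section states "We will not employ formal stopping rules" because the need is thought very unlikely. The next sentence opens with a contrast and a reference back to earlier text, and then says "we will temporarily halt enrollment if 3 AE occur so that we can identify potential causes before proceeding".

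**Section 7.5 (Safety Monitoring).** The monitoring board reviews events at 50% of expected enrollment, and the text expects that "it is highly unlikely that the use of stopping rules will be required". It also says that most complications and adverse events come from the surgery rather than the anesthesia.

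**Sections 7.1.1 and 7.2.1.** An AE is "any untoward medical occurrence associated with the use of an intervention in humans", related or not. All AEs are recorded regardless of relationship to study arm, from consent until 30 days after last participation.

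**The concern.** A site coordinator or board member who reads both sections cannot tell which events to count or what happens at the third one. Take three patients with a seroma found on examination, an event listed in 7.1.4. Under the literal wording of 9.3 they pause enrollment. Under Section 8 they count only if each is grade 3, is judged probably or definitely related to the anesthesia intervention, and is not classed as a surgical complication.

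The ambiguity can do harm in either direction. A broad reading could interrupt recruitment over minor events, and enrollment is itself a primary pilot outcome (9.1.4, 9.4.1). A narrow reading could mean that a pause promised in 9.3 never happens. In both cases, the rule concerns participant safety and should have one meaning.

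**Working it through.** **Step 1. The two sections side by side**

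| Element | Section 8 | Section 9.3 |
|---|---|---|
| Number of events | 3 | 3 |
| Severity | Grade 3; higher grades not mentioned | Not stated |
| Relatedness | Probably or definitely related to the study interventions | Not stated |
| Surgical complications | Excluded | Not stated |
| Consequence | Study halted; no new participants | Enrollment temporarily halted |
| Restart | No condition given | After causes are looked for; no one named to clear it |

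Only the count agrees. Where 9.3 is silent, the protocol's own AE definition (7.1.1) fills the gap, and that definition includes unrelated events. The surgical-complication row may matter most in practice, because 7.5 attributes most events to the surgery.

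A smaller point concerns grading. Section 7.2.2.1 describes some events as mild, moderate or severe and grades others by CTCAE version 5.0, so a trigger expressed as grade 3 does not map directly onto every event.

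**Step 2. How much the difference could matter**

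The plan states no probability for either trigger, so there is no figure to reproduce. The following is an illustration of the literal 9.3 wording.

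Inputs:
- n = 80: "Our goal for enrollment will be a total of 80 participants with 40 participants in each arm" (9.2.1).
- Threshold = 3 (9.3).
- p, the proportion of patients with any recorded AE: **an assumption**. The only rate in the safety plan is a risk below 1% in 7.5, and the type of event is unclear in the text. I use 1%, 5% and 10%.

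Formula, with X ~ Binomial(80, p):

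P(X ≥ 3) = 1 − [(1−p)^80 + 80·p·(1−p)^79 + 3160·p²·(1−p)^78]

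- p = 0.01: 1 − (0.4475 + 0.3616 + 0.1443) = 0.047
- p = 0.05: 1 − (0.0165 + 0.0695 + 0.1446) = 0.769
- p = 0.10: 1 − (0.0002 + 0.0019 + 0.0085) = 0.989

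A 95% chance needs p of about 7.7%. With n = 40, the point of the planned board review, the same three incidences give 0.008, 0.323 and 0.777.

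**Step 3. Limits of the illustration**

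- It counts patients ever affected. The 9.3 wording counts events, and one patient can have several, so on this score the figures are too low.
- It ignores timing. Surgery typically follows randomization by 4–6 weeks (6.2.2), and events are collected until 30 days after last participation (7.2.1). Events after the 24-month recruitment period (3.4) cannot pause enrollment, so on this score the figures are too high.
- The net direction cannot be settled from the documents.

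**The case against.** The strongest reply is that 9.3 is only a shortened restatement of Section 8. It refers back to something already set out, and Section 8 contains the only earlier numeric trigger. The consequences also overlap, since Section 8 closes screening to new participants. This is a plausible account of how the mismatch arose. It does not cure it: the shortened text drops every qualifier, the AE definition supplies a much broader meaning, and a study halt with no restart condition is not a temporary enrollment pause.

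A second reply is that oversight does not rest on this sentence. Serious events go to the IRB and NIA within 24 hours of identification (7.3.2), AEs are referred to the monitoring board (7.2.1), the board reviews at 50% enrollment (7.5), and the IRB or NIA can stop the study (11.4). That stands and limits the safety consequence, but none of these provisions says which halt applies.

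Two stronger readings are tempting, and the documents support neither:

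- **Three incompatible rules.** A reader might count the disclaimer of formal rules as a third version. In 9.3 it is joined by a contrast to the pause that follows, so it can be read as no statistical boundary but a safety pause. Section 7.5 only predicts that stopping rules will not be needed. The disclaimer sits awkwardly with Section 8's numeric halt, but the firm conflict is between two texts.
- **A near-certain halt.** A reader might infer that the 9.3 wording would almost certainly stop enrollment. That needs roughly 8–10% of patients to have a recorded AE. The broad definition, active questioning at each visit and six months of follow-up make such a rate plausible, but the documents do not give it. At 1% the chance is under 5%. The stated consequence is also temporary.

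**Conclusion.** Wrong as written. Sections 8 and 9.3 agree on the number three and on little else: severity, relatedness, treatment of surgical complications and consequence all differ or are left open, while 9.3 presents the two as one rule. This follows from the text alone and needs no assumption.

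The practical size is uncertain. The spread from 5% to 99% rests on an assumed AE incidence and on the simplifications listed in the working. It shows that the choice of reading could matter greatly; it does not predict that a halt will occur.

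**What to change.** Reconcile the passages into one trigger, stated once, that specifies:

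- the event grade, whether higher grades count, and how the mild/moderate/severe scale in 7.2.2.1 maps to it;
- the degree of relatedness required, if any;
- whether surgical complications count;
- the number of events;
- whether the consequence is a study halt or a temporary enrollment pause and, if enrollment can resume, on what condition and on whose decision.

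Cross-reference that statement from 7.5, 8 and 9.3 and delete the conflicting wording. If the disclaimer of formal stopping rules stays, say that it means no statistical boundary. Which rule applies is for the sponsor and the monitoring board to decide; this review proposes none. Stating the probability of triggering over 80 patients would help but is optional for a pilot.

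The cost is protocol wording and the IRB review that 11.1 requires for any modification. Sample size, data collection and analysis are unaffected.

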9.4 Outcomes

Discuss how the outcomes will be analyzed. Describe whether the documentation of an outcome will be reviewed and adjudicated by a committee, how quickly the committee will perform the adjudication, and whether the committee will be masked to the participant's intervention group assignment.

9.4.1 Primary outcomes

The primary outcomes are all pilot outcomes designed to demonstrate feasibility of conducting a multisite randomized clinical trial. The pilot outcomes, methods for measurement, and timing of measurement are outlined in **Table 2** (page 40).

- 1) Outcome: Rates of enrollment and percentage of eligible patients enrolled
 - a. Measurement: Each week, research assistants will compile running counts of patients who are screened, found eligible, and enrolled. Reasons for non-enrollment will be recorded. The measured outcomes will also be placed in graphical format to plot a comparison of expected versus actual rates for eligibility and enrollment.
 - b. Timing: The reports of numerical and graphical values will be reviewed every other week at our videoconference (Teams) team meeting that will include both study sites.
- 2) Outcome: Proportion of participants completing all study visits
 - a. Measurement: Research assistants will maintain running counts of participants who complete each study visit. We will evaluate rates of completing (attending) each study visit and calculate the final proportion of patients who complete all visits. This will be presented to the study team in numerical and graphical format
 - b. Timing: Reports will be reviewed at each every other week study team meeting.
- 3) Outcome: Proportion of missing data
 - a. Measurement: For each visit, every study instrument will be entered into our electronic database and missing items will have a separate code number (-

- 99) to facilitate easy counting of missing items vs total items to complete. Research assistants will generate a report showing overall percentage of missing data (number of missing items/current number of possible items for each patient) and the percent of missing data for each patient.
- b. Timing: Each bi-weekly team meeting will involve a review of missing data at the overall study and patient level.
- 4) Outcome: Time to complete study evaluations and instruments
 - a. Measurement: Research assistants will time participants while completing each study research form and will also time the entire encounter at each study visit.
 - b. Timing: Data will be collected at each visit and will be reviewed by the study team at the last team meeting of each month to establish reasonably stable estimates of time.
 - 5) Outcome: Participant satisfaction with study procedures and instruments
 - a. Measurement: At each visit, after completing all other study forms and procedures, participants will be asked to complete a brief 10-item Likert-type score to measure overall satisfaction with the study visit and a similar item assessing satisfaction with the time burden of the instruments. Additionally, we will conduct a brief interview with open-ended questions at the end of each visit asking patients to provide any feedback on the study procedures or instruments. These will not be recorded but field notes by the research assistant will be taken.
 - b. Timing: Assessments will occur at each study visit and will be reviewed at the last team meeting of each month.
 - 6) Outcome: Whether survey instruments can be eliminated due to redundancy
 - a. Measurement: To determine whether we can reduce the survey burden by eliminating redundant measures, we will employ methods outlined by Harrell for data reduction.²² Each survey instrument will be evaluated as the dependent variable in a separate linear regression with the scores of all other instruments used as predictors, along with demographic information. The adjusted R^2 (explained variance) for each regression will be estimated. Any instrument where the R^2 exceeds 40% will be eliminated based on the idea that little additional information is provided by including that instrument (i.e. the other surveys explain a substantial portion of the information contained within that instrument).
 - b. Timing: We will assess survey redundancy once 25% of planned enrollment is achieved and we will measure again at 75% enrollment. This will provide reasonable data stability for estimation and also provide time for us to test study procedures after eliminating any instruments that are found to be redundant.
 - 7) Outcome: Estimating sample size for fully powered trial
 - a. Measurement: For continuous variables, we will estimate means and standard deviations. For categorical variables, we will estimate proportions and 95% confidence intervals.
 - b. Timing: Final sample size estimate will be performed after data collection for the last patient is complete.

Table 2. Analysis of primary (pilot) outcomes		
Outcome	Measurement	Timing
Rate of enrollment and percent of eligible patients enrolled	
 Running count and graph of planned versus actual enrollment 	Team meeting (every other week)
Reasons for non-enrollment	
 Running count and graph 	Team meeting (every other week)
Proportion of participants completing all visits	
 Running count and graph 	Team meeting (every other week)
Proportion missing data	
 Running count and graph 	Team meeting (every other week)
Time to complete study evaluations and instruments	
 Research assistant uses timer during visit 	Once per month at team meeting
Participant satisfaction with procedures and instruments	
 10-point Likert-type scale Short interview at end of each visit 	Once per month at team meeting
Identify redundant instruments	
 Predict explained variance (R-squared) of each instrument from scores of other instruments 	At 25% and 75% enrollment
Identify areas of improvement for study procedures	
 Short patient interview at end of each visit Study team discussions at weekly meeting 	Team meeting (every other week)
Estimate sample size	
 Measures of dispersion (mean and standard deviation) Proportions and 95% confidence intervals 	After data collection for final patient is complete

State and define the primary outcome measure and specify at which study visit the outcome assessments will be performed.

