9.1.4 Primary outcomes and hypotheses

- 1) Outcome: Rates of enrollment
 - a. Hypothesis: Based on our preliminary data, at least 75% of eligible patients will agree to be randomized.
- 2) Outcome: Proportion of participants completing all study visits
 - a. Hypothesis: We will be able to follow 100% of patients up to their 2 week postoperative visit (as essentially all patients keep this appointment in our clinical practice), and we will be able to follow at least 90% of patients at the six month time point.
- 3) Outcome: Proportion of missing data
 - a. Hypothesis: Missing data on study instruments will be <5%
- 4) Outcome: Time to complete study evaluations and instruments
 - a. Hypothesis: Total time to complete each study evaluation will be acceptable to patients and <30 minutes.
- 5) Outcome: Participant satisfaction with study procedures and instruments
 - a. Hypothesis: Overall time burden for instrument completion will be acceptable to patients

- 6) Outcome: Whether survey instruments can be eliminated due to redundancy
 - b. Hypothesis: One or more study instruments can be eliminated (thus reducing the time burden) because the other instruments may predict a substantial portion of variance
- (7) Outcome: Estimate sample size for fully powered randomized trial.
 - a. Hypothesis 1: Using data from the pilot study, we will be able to establish stable estimates of the necessary sample size for a randomized trial.
 - b. Hypothesis 2: We will be able to identify the optimal primary outcome for a multisite randomized trial by balancing the necessary sample size needed to adequately power the study versus the clinical significance of each outcome.

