9.4.2 Secondary outcomes

Timing of measurements for secondary outcomes is outlined in the schedule of evaluations (section 6.1). Instruments are briefly summarized in [Table 3](#) below.

- 1) Outcome: Quality of life
 - a. Measurement: The Carolinas Comfort Scale (CCS) was developed specifically to measure quality of life in patients having hernia repair.²³ The instrument consists of 8 items on a 6-point Likert-type scale. The Cronbach's alpha was 0.979 in the original development paper and 0.95 on a subsequent international validation study.²¹ The CCS demonstrates superior discrimination when compared to generic quality of life instruments (SF-36), with reasonable test-retest reliability (kappa coefficients for questions range from 0.40-0.60 for all but 1 item. Additionally, the CCS is used as the primary quality of life instrument for the International Hernia Mesh Registry because it can be rapidly administered, is well accepted by patients, is highly reliable, and typically has only 10-15% missing data when used for the international registry.²¹ The CCS can be scored as a summary of all items and as a binary score for the presence or absence of symptoms. We will use a 0.5 standard deviation difference on the continuous scale as the minimal clinically important difference.²⁴
 - b. Timing: The CCS will be measured at baseline, 48 hours after surgery, at 2 weeks after surgery, and at 6 months after surgery.
- 2) Outcome: Physical function
 - a. Measurement: We will measure independence in activities of daily living with the 6-item Katz Index, a long-established measure for physical/functional status for individuals expected to have at least some degree of disability.²⁵ Prior work demonstrates coefficients of scalability ranging from 0.74-0.88, indicating the Katz Index offers a useful cumulative scale.²⁵ We will score the instrument on a 0-6 scale, indicating the number of activities where the participant is partially or fully dependent. A 0.5 standard deviation difference will again represent the minimal clinically important difference.²⁴
 - b. Timing: Measurement will occur at baseline, at 2 weeks after surgery, and at 6 months after surgery.
- 3) Outcome: Cognitive function and delirium
 - a. Measurement

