- a. Measurement: We will use a 10-point visual analog scale to measure overall pain levels. A 0.5 standard deviation will be considered a clinically significant difference.
 - b. Timing: Overall pain will be measured at baseline, prior to discharge, at 48 hours after surgery, at 2 weeks from surgery, and at 6 months from surgery.
- 5) Outcome: Postoperative complications
- a. Measurement: All complications will be recorded based on VA Surgical Quality Improvement Program definitions.³⁰ For complications not defined in VASQIP, definitions are also provided below.
 - i. Allergic reaction: if patients develop hives (raised red lesions) or a significant and persistent rash after administration of local or general anesthesia, this will be managed per the usual hospital protocol. Patients will receive a combination of epinephrine, corticosteroids, and antihistamines. Any patient with an allergic reaction will also be admitted for 24 hour observation that includes monitoring of vital signs, and blood pressure support with intravenous fluids. If the allergic reaction occurs during the operation, then the surgery will be canceled along with all assessments and will be rescheduled after it is determined that the operation can be performed safely without the allergic reaction.
 - ii. Hematoma or seroma: a collection of fluid in the tissues over the

incision site or in the scrotum that is detected on physical exam constitutes either a seroma or hematoma. If minimal symptoms present, this will be managed by observation. If persistent and significant symptoms occur, the seroma/hematoma will initially be managed by aspiration under local anesthesia up to two times. If the symptoms persist after aspiration, then the patient can be taken back to the operating room for surgical evacuation.

- iii. Injury to vessel: during dissection and/or mesh placement, there is the possibility of injury to the femoral or inferior epigastric vessels. If bleeding occurs at these vessels that cannot be resolved by applying pressure, this will be categorized as vascular injury. The inferior epigastric vessel is typically ligated without consequence if injured. Injury to femoral vessels will result in consult to vascular surgery for repair.

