- a. Measurement: Immediately following surgery, patients are typically transported directly to the post-anesthesia recovery unit for close monitoring by nursing staff and anesthesia faculty. Once the effects of anesthesia have diminished and patients are able to stay awake and maintain oxygenation without additional stimuli, they are transported to the stepdown unit for a period of observation to ensure they are able to ambulate and tolerate oral intake without nausea or vomiting. Time in the post-anesthesia care unit will be recorded as the difference between time of transport to the stepdown unit and the time of exit from the operating room. Time in the stepdown unit will be calculated as the difference between the time patients are discharged from the hospital (typically on the same day as surgery) and the time of transport from the post-anesthesia care unit. If patients are admitted rather than being discharged home on the same day as surgery, then stepdown time will be calculated as the difference between arrival in the inpatient or observation unit and the time of entrance to the stepdown unit. All values will be calculated in minutes.
 - b. Timing: These values will be calculated on the day of surgery by research assistants.

Table 3. Analysis of secondary (clinical outcomes)		
Outcome	Measurement	Number of items & time to completion
Quality of life	Carolinas Comfort Scale	8 items Time to completion: 1 minute
Physical function	Katz index	6 items Time to completion: 2 minutes
Cognitive function	1) Confusion Assessment Method (short form) 2) Montreal Cognitive Assessment 5-minute form 3) Trail Making Test Parts A and B	1) 4 items, time to completion 5 minutes 2) 8 items, time to completion 5 minutes 3) 2 trails, time to completion 2 minutes
Pain	Visual Analog Scale	1 item Time to completion: 10 seconds
Postoperative complications	VA Surgical Quality Improvement Program definitions	Complications outlined above Assessed by research assistants and not participants
Operative and anesthesia times	Time from anesthesia note	Assessed by research assistants and not participants

Recovery time in post-anesthesia care unit and stepdown unit	Timer by research assistant	Assessed by research assistants and not participants
--	-----------------------------	--

State and define the secondary outcome measures.

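### The <5% missing-data target is a pooled item percentage, so it can be met while a short instrument goes largely unmeasured

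*Combined protocol and SAP*

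**What the plan says.** Section 9.1.4 (outcome 3) states the target: "Missing data on study instruments will be <5" per cent. Section 1.1 gives the same hypothesis.

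Section 9.4.1 (outcome 3) defines the measurement. Every missing item is coded -99, and research assistants report the "overall percentage of missing data (number of missing items/current number of possible items for each patient) and the percent of missing data for each patient". On timing it adds: "Each bi-weekly team meeting will involve a review of missing data at the overall study and patient level".

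Table 2 adds only a running count and graph, and section 9.5.1 only simple descriptive statistics. No section asks for a percentage by instrument or by visit.

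The instruments differ widely in length. Table 3 lists pain as "1 item Time to completion: 10 seconds", against 8 items each for the Carolinas Comfort Scale (CCS) and the 5-minute MoCA. Section 9.4.2 also says of the CCS that it "typically has only 10-15% missing data when used for the international registry".

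**The concern.** The Précis names the ability to measure the relevant outcomes as part of the primary objective, and section 9.1.4 (outcome 7, hypothesis 2) intends to use the pilot to choose the primary outcome of the multisite trial. Both need to know, for each candidate outcome, how many participants yield a usable score. The clinical outcomes are compared as instrument scores, and section 9.5.3 makes complete-case analysis primary, so missingness matters at the level of instrument and visit.

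A pooled item percentage weights each instrument by its number of items. A one-item outcome such as pain carries one eighth of the weight of the CCS at the same visit. The figure can therefore stay under 5% while a short instrument is mostly or wholly missing.

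**Working it through.** The 5% is a fixed target, and the documents give no total item count to reproduce. The check is a direct count.

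**Inputs.** Items per administration come from Table 3 and, for FRAIL, section 6.2.2. Visits come from the section 6.1 schedule.

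| Instrument | Items | Visits | Items per patient | Share of 136 |
|---|---|---|---|---|
| MoCA, 5-minute | 8 | 5 | 40 | 29.4% |
| CCS | 8 | 4 | 32 | 23.5% |
| Katz | 6 | 4 | 24 | 17.6% |
| CAM | 4 | 5 | 20 | 14.7% |
| Trail Making A and B | 2 | 5 | 10 | 7.4% |
| Pain scale | 1 | 5 | 5 | 3.7% |
| FRAIL | 5 | 1 | 5 | 3.7% |

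By visit: 34 (baseline) + 15 (before discharge) + 29 (48 hours) + 29 (2 weeks) + 29 (6 months) = 136. Section 9.4.2 omits Katz at 48 hours, although sections 6.1 and 6.2.3 include it; without it the total is 136 − 6 = 130.

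**Formula.** Pooled percentage = missing items / possible items. Five per cent is 0.05 × 136 = 6.8 items per patient.

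**Pain missing in everyone at every visit.** 5/136 = 3.7%, or 5/130 = 3.8%. Over 80 patients this is 400/10,880 = 3.7%. Each patient's own figure is also 5/136 = 3.7%, so the patient-level report shows nothing unusual. The result does not depend on how the schedule is read:

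- Without Katz at 48 hours and without FRAIL: 5/125 = 4.0%.
- Pain not taken before discharge (section 6.2.3 does not list it at Visit 3): 4/135 = 3.0%.
- Post-baseline items only: 4/102 = 3.9%, or 4/96 = 4.2% without Katz at 48 hours.
- Satisfaction items counted as well (1 to 11 per visit): 5/141 = 3.5% down to 5/191 = 2.6%.

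With pain at five visits, the pooled figure reaches 5% only if the denominator is 100 items or fewer (5/0.05).

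**Trail Making missing in everyone at the remote visits.** Section 9.4.2 describes a test in which participants draw lines between circles. Section 6.2.3 conducts the 48-hour visit by phone, and section 6.2.4 the six-month visit by phone or video. The documents do not say how the test is given remotely. Losing it at both visits is 2 × 2 = 4 items: 4/136 = 2.9%, or 4/130 = 3.1%.

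**CCS at the cited 10–15%.** The documents do not say whether that range counts items, forms or patients. If it is read as items (an assumption), 3.2 to 4.8 of 32 items are missing, giving 3.2/136 = 2.4% to 4.8/136 = 3.5% pooled.

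**What would not pass.** Trail Making missing at all five visits is 10/136 = 7.4%, and the CCS missing in everyone at one visit is 8/136 = 5.9%. The pain example also leaves room for only 6.8 − 5 = 1.8 further missing items per patient.

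**Same losses counted by instrument,** assuming all 80 patients attend every visit: pain 400/400 = 100%; Trail Making 160/400 = 40%, with 100% shown at the two remote visits. Neither meets a 5% target.

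**The case against.** The strongest reply is that a total loss of pain data is an extreme case and could hardly go unnoticed. Pain is a term in the redundancy regressions at 25% and 75% enrollment (sections 9.4.1 and 9.5.1), which could not be fitted as written without it. Each form is timed, each case report form is signed by the site and project principal investigators (section 10.1), and a monitor checks completeness (section 10.3.5). Sample-size estimation (outcome 7) needs means and standard deviations. All of this stands. It means that the loss could come to light elsewhere; it does not make outcome 3 informative. The Trail Making example is less extreme, because it follows from the planned mode of the visits.

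A reader might infer three stronger points that the documents do not support.

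- *That the pilot would wrongly be declared feasible.* The target is a hypothesis analysed descriptively. There is no formal go/no-go rule, and other feasibility outcomes stand beside it.
- *That heavy loss at six months would be hidden.* All six-month items could be missing in 6.8/29 = 23% of patients before the pooled figure reached 5%. If the cause is missed visits, however, outcome 2 would show 77% completion against its target of at least 90%.
- *That the 5% limit should apply to every instrument at every visit, with missed visits counted as missing.* A pilot that exactly met the 90% six-month target would then fail every six-month instrument. There are also 29 instrument-by-visit cells (7 + 4 + 6 + 6 + 6), and with 80 patients a limit under 5% allows at most 3 missing in each. At a true rate of 2%, a cell passes with probability about 0.92, and all 29 with about 0.92^29 ≈ 0.10 if independent (both the rate and the independence are assumptions, for illustration).

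**Conclusion.** The point holds as a weakness in how primary outcome 3 is measured. Pain missing throughout gives 3.7–3.8% on the section 6.1 schedule, with and without Katz at 48 hours, and 2.6–4.2% over all the readings tried. Trail Making missing at both remote visits gives about 3%. Each meets the target, and the per-patient percentage has the same blind spot. These figures assume that the remaining data are complete or nearly so, and that items count as section 9.4.1 describes. Complete loss at every visit passes only for pain and for FRAIL, which is measured at baseline alone; the longer instruments would exceed 5%.

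Section 9.4.1 also leaves open whether items from a missed visit belong to the current number of possible items. The conclusion does not depend on this, but the denominator should be stated.

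**What to change.** Change section 9.4.1 (outcome 3), section 9.1.4 and Table 2 as follows.

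1. For each instrument at each visit, report the number of participants attending that visit whose score cannot be computed, divided by the number attending. State for each instrument when a partly completed form counts as not computable; the documents give no rule for partly completed questionnaires.
2. Judge the under-5% target for each instrument on that basis, pooled over its scheduled visits among attended visits, with the by-visit figures shown alongside.
3. Judge missed visits under outcome 2 and its 90% six-month target, so that they are not counted twice.
4. Keep the pooled item percentage, overall and per patient, as a descriptive figure only.

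The cost is protocol wording and a revised report template. No new data are needed, since the -99 codes allow the tabulation. The target becomes somewhat harder to meet for some instruments, possibly including the CCS.
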